Results from the proposed study could increase patient recovery at little or no increased cost. Normal saline and lactated ringer's solutions (1000 ml or CC) are similar costs (1.485 and 1.304 Payment Limits, respectively)¹⁶, and both are readily available in most hospital formularies. This study proposes comparing two readily-available, low-cost IV fluids on the basis of patient-reported quality of recovery in patients discharged from the ED.

The study **hypothesis** is emergency department patients receiving lactated ringer's solution will have an improved Quality of Recovery when compared patients receiving normal saline.

C. Study Objectives

C.1. Primary Aim

The primary objective of this study is to compare the quality of recovery in ED patients receiving lactated ringer's and normal saline IV solutions at 24 hours after ED discharge.

C.2. Secondary Aim

The secondary aim of the study is to describe differences in healthcare utilization after ED discharge between subjects in the control NS and intervention LR groups.

D. Study Design

D.1. Overview & Design Summary

This is a single-blind, randomized controlled trial in a single Midwestern emergency department with 60,000 patient visits per year. Enrollment of 156 subjects is planned. Subjects will be randomized to receive a single administration of two liters of either normal saline or lactated ringer's solution. Evaluations will occur at baseline, one day following ED discharge, and seven days following ED discharge.

Potential participants will be screened upon ED registration. Subjects will participate in study for seven days (during ED visit with two remote follow-up contacts at one and seven days). Total duration of the study is expected to be 12 weeks.

D.2. Subject Selection

Subjects will be recruited in the emergency department by two trained research assistants (RAs). Subjects will be recruited beginning in May 2017.

D.2.a. Inclusion Criteria

Patients (1) with a chief complaint of: nausea, vomiting or emesis, diarrhea, abdominal pain, dizziness, weakness, heat stroke or heat exhaustion, dehydration, fatigue, or volume depletion; (2) are deemed by their ED provider to be clinically able to receive two liters of fluid; (3) are being administered fluids by their ED treatment team; and (4) are decided to be likely to be discharged from the ED are eligible for the study.

D.2.a. Exclusion Criteria

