At the time of enrollment, baseline characteristics of subjects will be collected by RAs by in-person interview (pre-intervention QoR-40 score) and from electronic medical record (age, gender). Some baseline characters will be collected at the chart abstraction (ED encounter disposition [discharged from ED/admitted to hospital/admitted to ICU], ED diagnosis type [by organ system]).

D.4.a. Primary Endpoint

The primary outcome of this study will be the post-treatment survey score of the Quality of Recovery-40 (QoR-40, see Attachment H-2) validated survey tool^{18,19}. The survey has been used extensively in the surgery anesthesia literature to measure patient-

reported recovery across five independent domains: Comfort, Emotion, Physical Independence, Patient Support, and Pain. Survey scores range from 40 to 200.

RAs will administer the QoR-40 to subjects initially before any intervention is administered (“pre”). Twenty-four hours following discharge, the RAs will administer the survey again by telephone (“post”). During survey administration, RA will fill-out survey on paper, and it will later be entered into the electronic database. If patient does not answer, two additional phone calls will be made in the 24-48 hours following ED discharge. Time of “post” survey response will be recorded.

D.4.b. Secondary Endpoint

Secondary endpoints are designed to examine differences in healthcare administration between the NS control and LR intervention groups. Secondary endpoints will be assessed at two time points (1) at the 24-hour post-discharge phone call and (2) with a 7-day follow-up text message utilizing a two-way text messaging system.

The following secondary endpoints will be recorded:

- (A) Sought additional healthcare for same complaint,
- (B) Returned to an ED for same complaint,
- (C) Filled an ED prescription from visit of enrollment, and

Each endpoint will be a dichotomous (yes/no) response. No adjudication of “same complaint” will be performed by the research team, as the intention is to capture the patient’s interpretation of healthcare utilization from the illness.

D.4.c. Subgroups

No *a priori* subgroup analyses are planned. Any subgroup analyses performed will be solely for the purpose of hypothesis generation.

E. Statistical Plan

E.1. Sample Size Determination and Power

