Study accrual will be reported weekly by RAs. Study accrual is expected to be about 13 subjects per week. Full research team meetings will occur if study accrual falls below 80% of expected total accrual for any end-of-the-week accrual reports. The purpose of the meeting will be to develop and implement strategies to increase subject accrual. Potential solutions could include utilization of trained ED enrollers currently in the department, additional training and education of ED medical and nursing staff on the study, and recommendations to RAs by current clinicians on increasing visibility and awareness of the study during ED clinical shifts. Concerns will be addressed in a weekly meeting of RAs and investigators at enrollment site.

Safety reporting will occur after enrollment of every 30 subjects (the last group will be 36 subjects). If an adverse event is recorded, the Safety Coordinator will review the event within 24 hours. The local IRB will also be notified.

F.2. Data Review

Data from paper surveys and enrollment forms will be entered into a secure database by the RAs. At the end of enrollment and before analysis, one investigator will perform a 10% audit of the data. Concordance will be measured using a κ statistic. Following audit, the database will be locked for analysis.

G. Study Administration

G.1. Organization and Participating Centers

Enrollment for this single center study will occur at:

Emergency Treatment Center
Department of Emergency Medicine
University of Iowa Hospitals and Clinics
[name]
[name]

[figure not shown]
Investigators, study statistician, research assistants, and safety coordinator are affiliated with the University of Iowa.

H. Attachments

H.1. Procedure Table

Measure	Timeline				
	Baseline (Before Intervention)	During Intervention	Phone call: 24 hours after ED discharge	Text message: 7 days after ED discharge	Chart review: 28 days after ED discharge
Quality of Recovery-40	X		X		
Time and Amount of Fluid Administered		X			
Returned to ED for same complaint			X	X	
Sought additional healthcare for same complaint			X	X	
Filled ED prescription			X	X	
Adverse Event Monitoring		X	X	X	X

H.2. Primary Outcome Survey, “Quality of Recovery-40”¹⁸

I. References

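### ED disposition is listed as a baseline characteristic, so a post-randomisation result can trigger an adjusted analysis; the call to admitted subjects also needs one stated clock

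*Combined protocol and SAP*

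**What the plan says.** On disposition: section D.4 names "ED encounter disposition [discharged from ED/admitted to hospital/admitted to ICU", together with ED diagnosis type, among baseline items taken later at chart abstraction. Section E.2 (Baseline characteristics) tests such items between arms. A significant difference leads to an adjusted analysis of primary and secondary variables, meant to gauge the effect of the imbalance. The primary outcome itself is compared by t-test or Mann-Whitney test under ITT.

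On eligibility: section D.2.a asks only that patients "are decided to be likely to be discharged from the ED", so some randomised subjects may be admitted.

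On timing of the second QoR-40:
- Section C.1: "compare the quality of recovery in ED patients receiving lactated ringer's and normal saline IV solutions at 24 hours after ED discharge".
- Section D.4.a: "Twenty-four hours following discharge, the RAs will administer the survey again by telephone", with no mention of the ED in that sentence, and then "two additional phone calls will be made in the 24-48 hours following ED discharge" if the subject does not answer.
- Section H.1, procedure table: "Phone call: 24 hours after ED discharge".
- Section D.1, for all subjects without distinction: "during ED visit with two remote follow-up contacts at one and seven days".

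No section says whether or when an admitted subject is called.

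**The concern.** A baseline characteristic is fixed before treatment can act. ED disposition is settled after randomisation, and normally after the infusion, so it may partly be a consequence of the fluid. If arms differ on it, the rule in section E.2 produces an analysis that conditions on a possible effect of treatment and labels it a check on imbalance. Whatever part of the fluid's effect acts through admission is taken out of that estimate.

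The secondary point is one of clarity. The disposition list in section D.4 separates discharge from the ED from both kinds of admission, so a clock that starts at ED discharge does not plainly cover an admitted subject. The unqualified word in section D.4.a could even be read as discharge from hospital. If staff took the strict view and did not call admitted subjects, the nominal ITT comparison would be selected on an event after randomisation. Disposition by arm would show the imbalance, but there would be no scores with which to judge its effect.

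**Working it through.** **The plan's own figure.** Section E.1 gives 156 subjects for a 10-point difference, alpha 0.05, 20% dropout and a stated beta of 0.90, read here as power. No SD is given, so 156 cannot be reproduced independently. Working back: 156 × 0.8 = 124.8 evaluable, or 62.4 per arm. The two-sided normal approximation gives SD = 10 × √(62.4/2) / (1.960 + 1.282) = 17.23. With the t distribution, SD 17.04 gives power 0.902, and this value is used below. Standard error = 17.04 × √(2/62.4) = 3.05.

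**Assumptions not in the documents.** 78 randomised per arm (156/2, 1:1); admission NS vs LR of 8% vs 5%, or 15% vs 8%; a 20 to 30 point lower score in admitted subjects where a gap is needed. Expected admissions: 78 × (0.08 + 0.05) = 10.1 and 78 × (0.15 + 0.08) = 17.9.

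**1. How often the adjustment triggers.** Exact binomial calculation, Pearson chi-square p < 0.05, disposition collapsed to admitted or discharged:

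| Admission rates | Probability of trigger | Mean observed difference when triggered |
|---|---|---|
| 5% vs 5% | 0.049 | 0 |
| 8% vs 5% | 0.120 | 8.9 points of percentage |
| 15% vs 8% | 0.280 | 13.0 points of percentage |

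**2. What it does when triggered.** Take the extreme case in which the whole effect acts through admission. The true effect is gap × rate difference: 20 × 0.03 = 0.6, 30 × 0.03 = 0.9, 20 × 0.07 = 1.4, 30 × 0.07 = 2.1 points. The disposition-adjusted estimate averages about 0 in simulation (-0.09 to +0.02). The unadjusted estimate in the same trials is near gap × observed difference: 20 × 0.089 = 1.8, 30 × 0.089 = 2.7, 20 × 0.130 = 2.6, 30 × 0.130 = 3.9. Simulated averages are 1.8 to 2.6 and 2.5 to 3.9, the same within rounding and simulation noise.

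Triggered trials are selected for a large observed imbalance. Of that imbalance, (8.9 - 3)/8.9 = 66% in the first case and (13.0 - 7)/13.0 = 46% in the second is chance.

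**3. If admitted subjects were not called.** Suppose the sickest fraction p of each arm is admitted, admission itself changes no score, and severity correlates r with the outcome. The mean of those remaining shifts by r × SD × φ(z_p)/(1 - p), where φ is the normal density at the p-quantile. The ratio φ(z_p)/(1 - p) is 0.1086 at 5%, 0.1616 at 8% and 0.2743 at 15%. LR minus NS bias:
- 8% vs 5%: r × 17.04 × (0.1086 - 0.1616) = -0.27 (r = 0.3) or -0.45 (r = 0.5).
- 15% vs 8%: r × 17.04 × (0.1616 - 0.2743) = -0.58 or -0.96.
- Equal rates: 0. If LR has more admissions, the signs reverse.

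With no true effect on the score, dividing each bias by 3.05 moves the two-sided 5% error to 0.0509, 0.0525, 0.0541 and 0.0614.

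Steps 2 and 3 are alternatives and do not add up: if admitted subjects have no scores, discharged versus admitted does not vary among those analysed.

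**The case against.** The adjusted analysis is supplementary. It does not replace the ITT comparison, and the t-test or Mann-Whitney result stands whatever disposition shows. That is right, and it limits the point to how a secondary estimate is chosen and read.

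A reader might infer that the adjustment simply strips out a real effect. The arithmetic does not support that. In triggered trials at 8% vs 5%, the unadjusted estimate is too high by about 1.2 to 1.7 points (1.8 - 0.6, 2.6 - 0.9), while the adjusted one is too low by only 0.6 to 0.9. At 15% vs 8% the errors are about 1.1 to 1.8 too high and 1.4 to 2.1 too low. Much of what is removed is chance. What stands is the principle: the plan cannot tell chance from effect in a variable measured after randomisation, and should not call it baseline.

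A reader might also infer that admitted subjects are dropped and the ITT analysis is therefore invalid. The documents do not say so. Section D.1 gives every subject two remote contacts, section E.2 specifies ITT, and section H.1 times safety follow-up the same way, including "Chart review: 28 days after ED discharge". A strict reading would also remove scheduled safety follow-up from admitted subjects, which is implausible. Under the more natural reading the primary test is sound. What remains is that the wording admits more than one clock and never mentions admitted subjects.

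Finally, nothing in the documents suggests that admission will differ by arm. If it does not, the bias is about zero and the trigger fires at its nominal 5%.

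**Conclusion.** The baseline label is wrong as written and should be corrected. Severity is minor. The trigger rates of about 12% and 28% depend on assumed admission rates. The contrast between an adjusted estimate near 0 and true effects of 0.6 to 0.9 or 1.4 to 2.1 points further assumes that the whole effect acts through admission with a 20 to 30 point gap, which is the extreme case.

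The timing of the call to admitted subjects is a clarification, not a demonstrated flaw. Even if they were left out, the assumed bias of 0.3 to 1.0 point is at most about a third of a standard error (0.96/3.05 = 0.31) and a tenth of the 10-point target. Power stays about 90% if admissions fall within the 20% dropout allowance.

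**What to change.** 1. Remove ED disposition from the baseline characteristics that can trigger adjustment in section E.2, and report it by arm as a post-randomisation result. Treat ED diagnosis type, abstracted at the same point, the same way unless it is fixed before the infusion. This costs nothing.
2. State in section D.4.a, and match in sections C.1 and H.1, that admitted subjects receive the same blinded telephone call on one stated clock, for example from ED departure by any route. State that available scores from all randomised subjects enter the ITT comparison, with discharged-only as a sensitivity analysis.

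The second change adds no calls, and the exclusion criteria already require phone access for seven days. It has downsides. Some scores will be taken in hospital, and some will be missing because the subject is too ill; a t-test cannot include those, so the plan should say how missing scores are handled and report them by arm. The objective, framed in section B.2 around patients stable for discharge, needs slight rewording. The plan must also say how the prescription and healthcare-use endpoints are scored for admitted subjects. Time of ED departure is itself set after randomisation, but section E.2 already examines time from intervention to primary outcome.

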Sample size calculation was based on the detection of a 10-point difference on the QoR-40 survey scores. A 10-pt difference was selected as the minimum detectable difference maintaining clinical relevance, as supported by previous studies¹⁸⁻²¹. Sample size calculation ($\alpha = 0.05$, $\beta = 0.90$, 20% dropout, difference of 10 points) revealed a need for 156 total subjects.

E.2. Statistical Analysis

Baseline characteristics. Baseline characteristics will be reported with summary statistics as appropriate (mean, SD, median, IQR) and differences in characteristics will be conducted using t-test for continuous variables and chi-square test for categorical variables. If any baseline characteristics have significant differences, those behaviors will be reported in the results section and an adjusted analysis will be performed on primary and secondary variables to assess the impact of the imbalances.

Primary outcome. The primary outcome, pre-post difference in Quality of Recovery-40, will be analyzed using a t-test (if parametric) or Mann Whitney U Test (non-parametric) in an intention-to-treat (ITT) analysis. Due to the nature of emergency department

research, an additional analysis will be done by treatment received and compared to the primary ITT analysis.

Secondary outcome & safety analysis. Secondary outcomes will be reported as a relative risk with 95%CI in an ITT analysis. A safety analysis of selected secondary outcomes (return to ED and seeking additional healthcare for same complaint) will be performed by treatment received.

Covariate analysis. Differences in actual fluid administered and time from intervention to primary outcome will be assessed. If significant, analysis adjusting for covariates of time from intervention to primary outcome, post-QoR-40 administration, and amount of fluid (mL) received will be performed with multivariable linear regression and multivariable logistic regression (primary and secondary outcomes, respectively).

F. Quality Control

F.1. Study Monitoring Plan

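### Admission from the index ED visit can follow randomisation and compete with return to the ED, yet it is filed as a baseline characteristic and counted in no secondary or safety comparison.

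*Combined protocol and SAP*

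**What the plan says.** Section D.2.a makes disposition a forecast at entry: patients who "are decided to be likely to be discharged from the ED are eligible for the study". Randomisation and infusion take place during that visit (D.2.c, D.3), so the actual disposition may be settled after treatment.

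Section D.4 lists "ED encounter disposition [discharged from ED/admitted to hospital/admitted to ICU" among the baseline characteristics, to be taken from the chart later. Under E.2, baseline characteristics are tested between arms, and a significant difference leads to an adjusted analysis of the primary and secondary variables.

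The secondary aim (C.2) concerns utilisation after ED discharge. D.4.b gives three yes/no items: seeking additional healthcare, "Returned to an ED for same complaint", and filling an ED prescription. They are asked at the 24-hour call and in the 7-day text, both timed from ED discharge. The list in D.4.b ends on a dangling conjunction, but the procedure table in H.1 shows the same three utilisation items and none for admission.

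Section E.2 reports the secondary outcomes as relative risks with 95% CI by ITT, and adds: "A safety analysis of selected secondary outcomes (return to ED and seeking additional healthcare for same complaint) will be performed by treatment received".

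Neither D.4.b nor E.2 says whether a subject admitted from the index visit is a 'no', missing, excluded or an event on these items, or when that subject's 24-hour and 7-day clocks start.

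**The concern.** An index admission is heavy use of care, and it can occur after the fluid has been started. It is not itself a return to an ED, and it takes the subject out of risk of returning for part or all of the 7-day window. It is therefore a post-randomisation competing event for that endpoint.

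Two things follow. First, a difference in admissions between arms would be missing from every planned relative risk. Second, if admitted subjects are coded 'no' and kept in the denominator, more admissions in one arm lower that arm's return rate, so its return relative risk can look slightly better for the wrong reason. Treating disposition as baseline adds to the problem, because a possible effect of treatment would be handled as a chance imbalance to be adjusted away.

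**Working it through.** **Inputs from the documents.** Section E.1 "revealed a need for 156 total subjects". With 1:1 allocation (D.2.c) that is 156/2 = 78 per arm. The total agrees with 13 per week × 12 weeks = 156 (F.1, D.1) and with the safety batches 4 × 30 + 36 = 156 (F.1). The plan gives no admission rate, return rate or expected relative risk for the secondary endpoints, so there is no planned figure to reproduce for them.

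**Assumptions.** The return risk among discharged subjects is q = 15% in both arms. Index admission is a = 15% in arm Y and 5% in arm X. Admitted subjects keep a share s of the return risk within the window. All 78 per arm respond.

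**Formulas.**
- Return, all randomised subjects in the denominator: r = q(1 − a) + q·s·a
- Return, admitted subjects dropped: r = q
- Admission or return: c = a + q(1 − a). An admitted subject is already an event, so s does not enter.
- RR = Y/X, with 95% CI exp(ln RR ± 1.96·√[(1 − r_Y)/(78 r_Y) + (1 − r_X)/(78 r_X)])

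**Results.**
- s = 0: 0.85 × 0.15 = 0.1275 vs 0.95 × 0.15 = 0.1425. RR 0.89 (0.40 to 1.98), a difference of 0.015 × 78 = 1.2 expected returns.
- s = 0.5: 0.1388 vs 0.1463. RR 0.95.
- s = 1, or admitted subjects dropped: 0.15 vs 0.15. RR 1.00.
- Admission or return: 0.15 + 0.1275 = 0.2775 vs 0.05 + 0.1425 = 0.1925. RR 1.44 (0.81 to 2.57), a difference of 0.085 × 78 = 6.6 expected subjects.

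**Range.** With s = 0, q cancels and the return RR is (1 − a_Y)/(1 − a_X). Against 5% in arm X, admissions of 10%, 15% and 20% give 0.95, 0.89 and 0.84. Over q = 10% to 20% and the same admissions, the combined RR runs from 1.17 to 1.93. At q = 15% and admissions of 10% vs 5%, the pair is 0.135/0.1425 = 0.95 and 0.235/0.1925 = 1.22.

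**If sicker subjects are the ones admitted.** Suppose 30% of arm Y and 20% of arm X do badly, and 60% and 25% of these are admitted at once while the rest return. Admissions are 0.30 × 0.60 = 18% and 0.20 × 0.25 = 5%. Returns are 12% and 15%, RR 0.80, while the RR for doing badly is 0.30/0.20 = 1.50. Dropping admitted subjects no longer gives the risk ratio for doing badly: 0.12/0.82 = 0.146 vs 0.15/0.95 = 0.158, RR 0.93.

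**Would the baseline comparison show it?** Rounded to whole subjects, 15% vs 5% is 12/78 vs 4/78: chi-square p = 0.035, or 0.065 with continuity correction. For 10% vs 5%, 8/78 vs 4/78, p = 0.23 uncorrected. A doubling of admissions would pass unflagged, and a tripling might.

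**Additional healthcare.** D.4.b leaves the meaning of this item to the patient, without adjudication. An admitted subject may answer yes or no, so the text fixes no direction of bias.

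**The case against.** The strongest case on the other side has five parts.

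- *A reader might infer that an admitted subject can never count as a return.* That is true of the admission but not of the subject. After a short stay a subject can still return to an ED before the 7-day text, and the RR of 0.89 holds only if none can.
- *A reader might infer that the plan scores the worst course as event-free.* It does not say so. It states no coding, and if admission is unrelated to the risk of return, dropping admitted subjects gives 1.00. The defect is a missing rule together with a missing outcome.
- *A reader might infer that both safety items favour the arm with more admissions.* This is not established for additional healthcare, where a yes from admitted subjects would push the other way.
- *Admissions are not hidden.* Disposition is abstracted and tested between arms. Adverse events are monitored through to the 28-day chart review (H.1), and an outside physician sees 28-day data by masked group (D.3.c). This stands as far as visibility goes. However, the physician's review serves stopping decisions and covers only the enrolling facility, and the baseline test leads to adjustment for a post-randomisation variable. Neither is a planned between-arm outcome analysis.
- *The stated aim is utilisation after ED discharge.* Replacing return to the ED with a composite would answer a different question, and forcing admission to count as additional healthcare would override the patient-interpretation rule. Both objections stand, so the fix below does neither.

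**Conclusion.** The point holds as an omitted outcome and an unstated rule. Index admission is a post-randomisation competing event for return to the ED, and no planned secondary or safety comparison counts it. The possible distortion of the return RR is modest: 0.89 to 1.00 in the main illustration, with an interval at 78 per arm that comfortably includes 1. The larger loss is what goes uncounted, since admission-or-return has an RR of 1.44 under the same assumptions.

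All of this rests on assumed rates, on admissions differing between arms, and, for an RR below 1, on how admitted subjects are coded and how far they remain at risk. The documents do not show that fluid choice affects admission. They also do not support a forecast that the trial will report a favourable safety result for the worse arm. The change should be made because the gap is real and closing it costs very little.

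**What to change.** - In D.4, move index-visit disposition from the baseline characteristics to the outcomes. This also removes it from the baseline test and the adjustment that would follow.
- In D.4.b and E.2, report hospital or ICU admission from the index visit by arm as a utilisation and safety outcome: RR with 95% CI, by ITT and by treatment received.
- Add index admission or return to an ED for the same complaint within 7 days as a further outcome, with each component shown. Place it alongside the return-to-ED endpoint, which stays.
- State how admitted subjects are coded on the return item, whether they stay in the denominator, and when their 24-hour and 7-day clocks start. The composite does not depend on this choice, because an admitted subject is already an event.
- Leave additional healthcare as reported by the patient.

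The cost is protocol wording and one derived variable. Disposition is already abstracted, so no new data are needed. The small downside is one more secondary outcome and a composite that mixes events of different severity, which is why the components must be shown.

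### Section E.1 prints beta = 0.90 (10% power as written) and gives no SD, sidedness or form of endpoint, so the 90% power almost certainly meant cannot be verified

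*Combined protocol and SAP*

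**What the plan says.** The calculation is in section E.1. It begins: "Sample size calculation was based on the detection of a 10-point difference on the QoR-40 survey scores". The inputs follow in one parenthesis: alpha 0.05, then "\beta = 0.90$, 20% dropout, difference of 10 points) revealed a need for 156 total subjects". That is the complete list. Earlier studies are cited in support of the 10 points, but no SD is quoted from them, and no SD for the QoR-40 appears elsewhere in the document.

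The primary outcome is defined in two ways:

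- D.4.a: "The primary outcome of this study will be the post-treatment survey score of the Quality of Recovery-40".
- E.2: "The primary outcome, pre-post difference in Quality of Recovery-40, will be analyzed", by t-test or Mann-Whitney test.

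On direction, the hypothesis closing section B.2 is that the lactated Ringer's group "will have an improved Quality of Recovery when compared patients receiving normal saline". The primary aim in C.1 is neutral and speaks only of comparing the two fluids. Neither E.1 nor E.2 says whether the test is one- or two-sided.

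**The concern.** There are two problems in the same sentence.

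First, power is 1 - beta, so beta = 0.90 means a 90% chance of missing the target difference. It is the only power figure in the plan, and it is wrong as written.

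Second, correcting it to 90% does not make the claim checkable. A sample size for a difference in means cannot be computed without an SD, and the SD depends on which endpoint is meant. Under randomisation the expected difference between arms is the same for the post score and for the change from baseline, but their SDs generally differ. A calculation made for one does not carry over to the other.

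If the trial finds no difference, readers will ask whether it could have detected 10 points. At present the plan does not allow an answer.

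**Working it through.** **Inputs from the documents.** Alpha 0.05, difference 10 points, dropout 20%, total 156 (E.1); allocation 1:1 (D.2.c); score range 40 to 200 (D.4.a).

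**Assumptions.** SD, pre-post correlation, sidedness and dropout formula are not given, so they are shown as ranges. Evaluable per arm: 156 × 0.8 = 124.8, or 62 per arm rounded down. Power uses the noncentral t distribution with 122 degrees of freedom and noncentrality 10 / (SD × √(2/62)).

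**1. The printed figure taken literally.** For 10% power at 62 per arm, the SD would have to be about 85 two-sided or 152 one-sided. The largest SD a single score on a 40 to 200 scale can have is (200 - 40)/2 = 80. A change score has a wider range, so it is not strictly excluded, but 10/85 is about 0.12 SD, an implausible design target. Conversely, with an SD of 17, 10% power two-sided would need only 6 evaluable subjects in total (normal approximation). The entry is a mislabelled power.

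**2. Reproducing 156 at 90% power.** With SD 17 and a two-sided test, the smallest n with 90% power is 62 per arm. Then 62/0.8 = 77.5, rounded up to 78 per arm, or 156. Rounding matters: inflating the total gives 124/0.8 = 155, and the normal approximation gives 61 per arm and 122/0.8 = 152.5, or 153.

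**3. Other inputs that also give 156.** Each row uses the t-based n for 90% power, inflated and rounded up per arm. The last column is the power of a two-sided test at 62 per arm if that SD is correct.

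| Sidedness in the calculation | Dropout formula | SD that gives 156 | Two-sided power, 62 per arm |
|---|---|---|---|
| Two-sided | n / 0.8 | 16.91–17.04 | 90% |
| Two-sided | n × 1.2 | 17.32–17.45 | 89% |
| One-sided | n / 0.8 | 18.77–18.92 | 83–84% |
| One-sided | n × 1.2 | 19.23–19.37 | 81–82% |

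**4. Power for 10 points at 62 per arm, by SD of the endpoint analysed.**

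| SD | Two-sided | One-sided |
|---|---|---|
| 15 | 95.8% | 98.0% |
| 17 | 90.1% | 94.7% |
| 18 | 86.6% | 92.4% |
| 20 | 78.9% | 86.9% |
| 22 | 70.9% | 80.8% |
| 25 | 59.9% | 71.6% |

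Power is at least 90% when the SD is no more than 17.04 (two-sided) or 18.92 (one-sided).

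**5. If the SD was for the post score but the change is analysed.** With equal pre and post SDs of 17 (assumed) and pre-post correlation r, the SD of the change is 17 × √(2(1 - r)).

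| r | SD of change | Two-sided power |
|---|---|---|
| 0.3 | 20.11 | 78.4% |
| 0.4 | 18.62 | 84.3% |
| 0.5 | 17.00 | 90.1% |
| 0.6 | 15.21 | 95.3% |
| 0.7 | 13.17 | 98.7% |

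Break-even is at r = 0.5. Below it the change score loses power; above it, power is gained.

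**The case against.** The strongest reply is that this is a slip of notation plus thin reporting. Few readers would believe that a trial was designed for 10% power, and no arithmetic error in 156 has been shown. Two-sided testing at 0.05 is the ordinary reading: the aim in C.1 is neutral, E.2 names standard tests with 95% intervals for the secondary outcomes, and nothing proposes a one-sided test. The conflict between D.4.a and E.2 is a defect in its own right that would remain if E.1 were complete. A null result is in any case read mainly from its estimate and confidence interval.

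Much of this is fair. The beta entry is very probably a slip, 156 may well be right, and the one-sided rows have little support in the text. The exact SD intervals depend on the rounding convention, and all the power figures are for the t-test, although E.2 also allows Mann-Whitney. On its own, a missing SD or dropout formula would be a request for detail.

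Two things survive. The only stated power figure is wrong as printed. Once it is corrected, the 10-point claim is still not tied to a single endpoint, because the plan names two.

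**Conclusion.** The concern holds. As printed, E.1 states 10% power; 90% was almost certainly meant. Whether 156 subjects give 90% for the planned analysis cannot be determined from the documents.

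On the ordinary two-sided reading, with a t-test and 62 evaluable per arm, the claim is true only if the SD of the endpoint analysed is about 17.0 or less. A mismatch between post score and change could move power from 90% to anywhere between 78% and 99% for correlations of 0.3 to 0.7, with an assumed SD of 17. No SD or correlation is in the documents, so these are ranges, not estimates. This is a mislabelled figure and an uncheckable calculation; it does not show that the trial is underpowered. It should be corrected.

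**What to change.** In E.1:

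- Replace the beta entry with power = 0.90 (beta = 0.10), if that is what was used.
- State the sidedness, the SD used with its source, and the dropout formula with its rounding.

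In D.4.a and E.2, name the same primary endpoint, and say in E.1 that the 10 points and the SD refer to it. If that is the change score, give the SD of the change, or the assumed pre-post correlation from which it follows. Then restate the power that 156 enrolled, about 124 evaluable, gives for that endpoint and test. The sponsor should report its own inputs and not adopt the SD of 17 reconstructed here.

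The cost is a corrected sentence in E.1 and one endpoint definition reconciled between two sections. The correction does not itself call for more enrolment. The restated power may prove lower than 90%, or higher.
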